6.3 Subject Exclusion Criteria

- ^{131}I therapy < 6 months prior to initiation of therapy on this protocol. A diagnostic study using < 10 mCi of ^{131}I is not considered ^{131}I therapy. Any previous treatment with a PD1 or PD-L1 inhibitor, including durvalumab.
- History of pneumonitis.
- External beam radiation therapy < 4 weeks prior to initiation of therapy on this protocol..
- Chemotherapy, immunotherapy, targeted therapy, monoclonal antibodies, tumor embolization, or other investigational agent within 28 days prior to the first dose of study drug.
- Current or prior use of immunosuppressive medication within 28 days before the first dose of durvalumab, with the exceptions of intranasal and inhaled corticosteroids or systemic corticosteroids at physiological doses, which are not to exceed 10 mg/day of prednisone, or an equivalent corticosteroid.
- Any unresolved toxicity CTCAE grade ≥ 2 from previous anti-cancer therapy. Exceptions include hearing loss, peripheral neuropathy, and alopecia.
- Any prior Grade ≥ 3 immune-related adverse event (irAE) while receiving any previous immunotherapy agent, or any unresolved irAE $>$ Grade 1.
- Active or prior documented autoimmune disease within the past 2 years. NOTE: Subjects with a history of autoimmune thyroid disease are not excluded. Subjects with vitiligo or psoriasis not requiring systemic treatment (within the past 2 years) are not excluded.
- Active or prior documented inflammatory bowel disease (e.g., Crohn's disease, ulcerative colitis).
- History of primary immunodeficiency.
- History of allogeneic organ transplant.
- History of hypersensitivity to durvalumab or any excipient.
- History of hypersensitivity to thyrotropin alpha (Thyrogen).
- Patients unable to follow a low iodine diet or requiring medication with high content in iodide (amiodarone).
- Uncontrolled intercurrent illness including, but not limited to, ongoing or active infection, symptomatic congestive heart failure, uncontrolled hypertension, unstable angina pectoris, cardiac arrhythmia, active peptic ulcer disease or gastritis, active bleeding diatheses, acute or chronic hepatitis B, hepatitis C or human immunodeficiency virus (HIV), or psychiatric illness/social situations that would limit compliance with study requirements or compromise the ability of the subject to give written informed consent.

- Known history of active tuberculosis
- Symptomatic brain metastases, leptomeningeal carcinomatosis, or spinal cord compression (treated metastatic brain, leptomeningeal carcinomatosis, or spinal cord compression are allowed). Note: Patients must be off steroids used for brain metastases, leptomeningeal carcinomatosis, or spinal cord compression.
- Receipt of live attenuated vaccination within 30 days prior to study entry or within 30 days of receiving durvalumab.
- Female subjects who are pregnant, breast-feeding or male or female patients of reproductive potential who are not employing an effective method of birth control.
- Any condition that, in the opinion of the investigator, would interfere with evaluation of study treatment or interpretation of patient safety or study results
- Subjects with uncontrolled seizures.

7.0 RECRUITMENT PLAN

Potential research subjects will be identified by a member of the patient's treatment team, the protocol investigator, or research team. Patient recruitment most likely will occur in the medical oncology and endocrinology clinics of the Head and Neck Disease management team. If the investigator is a member of the treatment team, s/he will screen their patient's medical records for suitable research study participants and discuss the study and their potential for enrolling in the research study. Potential subjects contacted by their treating physician will be referred to the investigator/research staff of the study. Investigators will discuss the study and review/sign the informed consent documents with the patient.

During the initial conversation between the investigator/research staff and the patient, the patient may be asked to provide certain health information that is necessary to the recruitment and enrollment process. The investigator/research staff may also review portions of their medical records in order to further assess eligibility. They will use the information provided by the patient and/or medical record to confirm that the patient is eligible and to contact the patient regarding study enrollment. If the patient turns out to be ineligible for the research study, the research staff will destroy all information collected on the patient during the initial conversation and medical records review.

8.1 PRETREATMENT EVALUATION

Within 4 weeks of starting on study, the following tests/evaluations need to be done:

- Signing the Informed Consent Form.
- History and Physical Examination.
- Vital signs (pulse, blood pressure), including weight.
- Performance Status (Eastern Cooperative Oncology Group (ECOG) or Karnofsky Performance Status (KPS)) designation.
- Electrocardiogram (ECG or EKG) in triplicate.
- Radiology studies (CT(s) without contrast and/or MRI(s)) for disease assessment).
- Recording concurrent medications.

- Confirm availability of archival tumor tissue (if tissue is not already available at MSK, physical receipt of tissue is not required for study enrollment or initiation).
- Research tumor biopsy: The research biopsy will be performed any time prior to Week 1 Day 1 (can completed > 4 weeks before starting on study). Radiologic guidance (CT, MRI or ultrasound guided) approaches and obtaining multiple cores to ensure sufficient biopsy material (at least 3 cores preferred) are allowed as long as it is considered safe for the patient (image-guided biopsies will be performed by a radiology physician with the appropriate expertise).
- Research blood draw: Any time prior to start of study, approximately 10 mL of blood, preferably in a lavender top tube (with EDTA).
- Hematology tests (see Section 10).
- Clinical chemistry tests (see Section 10).
- Urinalysis (see Section 10).
- Pregnancy test in women of child-bearing potential (serum or urine beta-hCG within 7 days of starting the study).

9.1 TREATMENT/INTERVENTION PLAN

9.2 Concomitant Medications

The following medications are considered exclusionary during the study.

1. Any investigational anticancer therapy.
2. Any concurrent chemotherapy, radiotherapy (except palliative radiotherapy), immunotherapy, biologic or hormonal therapy for cancer treatment, other than TSH suppressive therapy and/or bisphosphonates and/or denosumab.
3. Immunosuppressive medications including, but not limited to, systemic corticosteroids at doses exceeding 10 mg/day of prednisone or equivalent, methotrexate, azathioprine, and TNF- α blockers. Use of immunosuppressive medications for the management of investigational product-related AEs or in subjects with contrast allergies is acceptable. In addition, use of inhaled and intranasal corticosteroids is permitted. A temporary period of steroids will be allowed for different indications, at the discretion of the principal investigator (e.g., chronic obstructive pulmonary disease, radiation, nausea, etc).
4. Live attenuated vaccines within 30 days of durvalumab dosing (i.e., 30 days prior to the first dose, during treatment with durvalumab and for 30 days post discontinuation of durvalumab). Inactivated vaccines, such as the injectable influenza vaccine, are permitted.

Contraception

Females of childbearing potential who are sexually active with a nonsterilised male partner must use at least 1 highly effective method of contraception (Table 1) from the time of screening, and must agree to continue using such precautions at least 90 days following the last infusion of durvalumab and avoid pregnancy for 9 months after RAI (¹³¹I) administration; cessation of birth control after this point should be discussed with a responsible physician. Periodic abstinence, the rhythm method, and the withdrawal method are not acceptable methods of birth control.

1. Females of childbearing potential are defined as those who are not surgically sterile (i.e., bilateral tubal ligation, bilateral oophorectomy, or complete hysterectomy) or postmenopausal (defined as 12 months with no menses without an alternative medical cause).
2. Subjects must use 2 acceptable methods of effective contraception as described in Table 1.
3. Nonsterilised males who are sexually active with a female partner of childbearing potential must use 2 acceptable methods of effective contraception (see Table 1) from Day 1 and for 90 days after receipt of the final dose of investigational product. Males should avoid impregnating females partners for 9 months after RAI (¹³¹I).

Table 1: Highly Effective^a Methods of Contraception

Barrier/Intrauterine Methods	Hormonal Methods

• Male condom plus spermicide• Copper T intrauterine device• Levonorgesterel-releasing intrauterine system (eg, Mirena[®])^b	
• Etonogestrel implants: e.g. Implanon or Norplan• Intravaginal device: e.g. ethinylestradiol and etonogestrel• Medroxyprogesterone injection: e.g. Depo-Provera• Normal and low dose combined oral contraceptive pill• Norelgestromin/ethinylestradiol transdermal system• Cerazette (desogestrel)

^a Highly effective (i.e. failure rate of <1% per year)

^b This is also considered a hormonal method

Blood donation

Subjects should not donate blood while participating in this study for at least 90 days following the last infusion of durvalumab and a minimum 12 months after administration of RAI.

9.3 Schedule of Events

- Patients will initiate treatment with durvalumab on Week 1, Day 1. The required evaluations and laboratory tests (detailed in **Section 10**) can be performed up to 7 days prior to initiation of treatment. It is unnecessary to repeat laboratory tests if the screening assessments of the same tests were performed within 7 days prior to first dose of therapy. Durvalumab 1500 mg IV

approximately every 4 weeks will be administered (adjustment to the dose may be necessary for patients weighing <30 kg). All other Week 1 evaluations (detailed in **Section 10**) may be performed up to 3 days prior to initiation of study treatment.

- In Cycle 1/Week 3, Thyrogen 0.9 mg IM will be administered on two consecutive calendar days followed by 100 mCi (+/- 10 mCi) RAI the next calendar day (these agents will be administered in clinic). The laboratory tests detailed in **Section 10** are to be drawn prior to the first Thyrogen injection.
- Research tumor biopsy: If after performance of the first research biopsy the investigator judges that it is safe to proceed with a second research biopsy, it is preferred that the procedure be performed during Cycle 2, Week 3 or 4 (though alternate timing for this second biopsy during Cycle 2 or later is allowed per investigator discretion or for safety reasons related to RAI administration). Biopsy of the same tumor that was sampled previously is preferred, but not required. Radiologic guidance (CT, MRI or ultrasound guided) approaches and obtaining multiple cores to ensure sufficient biopsy material (at least 3 cores preferred) are allowed as long as it is considered safe for the patient (image-guided biopsies will be performed by a radiology physician with the appropriate expertise).
- DLT monitoring and evaluations (including research blood collections) are to be conducted according to the schedule detailed in **Section 10**. Guidelines for holding durvalumab will be performed as outlined in **Section 11** and **Appendix 1**.

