Though ^{131}I can be particularly effective for treating small volume (< 1 cm), metastatic RAI-avid (RAIA; tumors with detectable RAI uptake) disease³, efficacy is significantly lower for patients with larger, structurally evident disease. Sabra et. al. published a retrospective study evaluating the efficacy of first-line ^{131}I therapy and reported that for these patients the rate of response with RAI was only 22%⁴. This observation is consistent with the 10% to 24% response rates reported in other retrospective series for similar subsets of patients^{3,5-7}. Though repeated administration of RAI is often possible, unfortunately many patients with metastatic tumors lose the ability to trap iodine, leading to RAI-refractory (RAIR) disease. This is associated with a worse prognosis (10% 10-year survival³), and systemic therapy options being limited to tyrosine kinase inhibitors (TKIs)^{8,9}.

With regards to clinical terminology, the “RAI-avid” designation is often used to not only describe the ability of tumors to incorporate RAI, but also infers that such tumors are responsive to RAI therapy. However, RAI avidity is not a binary variable, but a continuous one, and the clinical reality is that the degree of avidity encountered varies broadly from patient to patient, and indeed tumor to tumor. Since RAI efficacy is ultimately dependent upon the capability of thyroid tumors to take up and retain sufficient isotope to deliver tumoricidal doses of radiation, some RAI-refractory tumors are still “RAI-avid” in that isotope uptake can be identified on diagnostic scans¹⁰. In this protocol,

the term “RAI-avid” (RAIA) is limited to designating tumors that retain the ability to take up and retain iodide, and does not communicate the degree of avidity or sensitivity to RAI treatment (“RAI-avid” here can include both RAI-sensitive and –refractory patients). This RAIA patient population is the cohort that will be evaluated in this clinical trial.

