Of particular importance is the lack of data addressing how immune checkpoint inhibition and RAI therapy impacts the dynamics of the thyroid cancer immune microenvironment and genomic landscape. For the latter, immunotherapy induced changes to the tumor genome could provide insights into the “immunoediting” induced by therapy and potentially identify epitopes of particular significance for efficacy. The only approach that will provide new insight into these biologic processes is the analysis of serial research biopsies performed during therapy. On this study, biopsies will be performed pre-treatment and after durvalumab/RAI in Cycle 2. These tissues will be analyzed with next-generation sequencing of DNA and RNA. For cases in which sufficient tissue is collected, the immune microenvironment may be characterized by cytometric techniques, including flow cytometry or mass cytometry (CyTOF; MIBI). Protein based approaches, including IHC (e.g. for PD-L1, PD-L2 status), will also be employed. We hypothesize that durvalumab and RAI will increase tumoral immune infiltration characterized by enhanced markers of T cell activation (increased granzyme/performin expression, enrichment of the IFN-gamma signaling pathway, decreased Treg/CD8+ ratio). Beyond characterizing the tumor-associated T cell infiltrate, therapy induced changes of other immune cell populations will be examined (e.g. macrophages, NK cells, B-cells). Additionally, how durvalumab/RAI impacts the status of other immune checkpoint molecules (e.g. LAG-3, CTLA-4, TIM-3) may provide insights into putative mechanisms of resistance to this therapeutic approach. Such studies will be essential for rationally developing future immunotherapy based therapeutic approaches for advanced thyroid cancer patients.

Approach: The research biopsy samples will be divided for fixation and flash freezing at the discretion of the Principle Investigator. These samples will be used to evaluate the genomic and transcriptomic landscape of the tumors. Archival tissues may also be used if of sufficient quantity and quality.

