DNA and RNA will be extracted from frozen samples and/or paraffin tissue. The research peripheral blood sample collected on the study will be used as a control, matched normal sample (microdissection of normal tissue in the tumor samples may also be used for this purpose). DNA will be submitted for next generation sequencing, possibly whole exome or whole genome sequencing. The specific assay that will be employed to analyze for genomic alterations will be dependent upon the technology available at the time of analysis. Comparisons of DNA between tumor and normal tissue (from the research blood draw) will be performed as appropriate, thus generating germline sequence data. There is no intention to analyze the germline data beyond

utilizing it as a normal control for the tumor tissue analysis, and generally germline data will not be communicated to the patient. This data will be used to quantitate mutation load and identify candidate neoantigens.

Extracted RNA will be analyzed with RNAseq technology, or alternative assays, depending on technical limitations and assay availability. RNAseq data will be used to define a set of expressed neoepitopes and explore gene expression signatures that may correlate with response. RNAseq data analysis may include:

- Quantification of the following: 1) Markers of the MAPK pathway transcriptional output (e.g. Etv1, Etv4, Etv5, Spry2, Spry4, Dusp6); 2) Genes required for thyroid hormone biosynthesis (e.g. Nkx2.1, Pax8, Foxe1, Tg, Tpo, TshR, Nis, Pendrin, Dio2); 3) PD-L1 expression (PD-L1 expression will also be analyzed by IHC).
- Analysis to characterize tumor (a) immune cell infiltration and (b) immunologic gene signatures.

For patients in whom two serial research biopsies are obtained, evolution of the mutation, neoantigen, and gene expression landscape in pre- and post-treatment samples will be analyzed to gain insights into immunoediting that may occur and infer what epitopes may be critical for efficacy. RNAseq data will also be used to explore changes in the expression of nonmutated thyroid gene expression (e.g. TG, THSR, TPO, etc...) with therapy for the same purpose. The same data can be analyzed to evaluate how immune cell tumoral infiltration and immunologic gene signatures may change with therapy.

Frozen tissues from the research biopsy may be evaluated for relevant protein targets by Western blot or other proteomic assays that may be available at time of analysis.

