Mutation burden, neoantigen landscape, and immunoediting analysis: While the low DTC mutation burden implies a low likelihood of neoantigen formation, neoantigen analysis has never been conducted for DTC. Whole-exome sequencing data will be analyzed using the neoepitope bioinformatics pipeline developed by [name] group. Mutation calling is performed by analyzing FASTQ files with four mutation callers and filtering by allelic frequency, call quality and other empiric measures. Mutations are validated with an orthogonal next-gen sequencing panel. Candidate neoantigens are identified based on peptide sequences and predicted binding to patient-specific MHC Class I alleles. RNAseq data will be used to define a set of expressed neoepitopes and explore gene expression signatures that may correlate with response. Evolution of the mutation, neoantigen, and gene expression landscape in pre- and post-treatment samples will be analyzed to gain insights into immunoediting that may occur and infer what epitopes may be critical for efficacy. RNAseq data will also be used to explore changes in the expression of nonmutated thyroid gene expression (TG, THSR, TPO, etc...) with therapy for the same purpose. *Biostatistical analysis:* Categorical pre- and post-treatment measures will be summarized by 2-by-2 tables; continuous pre- and post-treatment measures will be summarized by mean and standard deviation of the change as well as graphical method.

Immune cell infiltrate and immunologic gene signature analysis: Tumor RNAseq data will be used to analyze changes in (a) immune cell infiltration and (b) immunologic gene signatures with therapy. First, we will estimate the relative infiltration levels of individual immune cell populations in tumor samples using two computational approaches. The first was developed by [name] and [name] at MSK which uses single set enrichment analysis (ssGSEA) to determine the abundance of T cell and other immune cell populations in the tumor microenvironment³². A related but alternative approach uses support vector regression to model cellular populations based on a reference expression matrix³³. These techniques provide efficient and accurate alternatives to flow cytometry sorting. In addition, RNAseq data permits quantification of related immunologic gene expression signatures such as IFNy signaling, granzyme B, and antigen presenting machinery genes.

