Intratumor heterogeneity analysis: Recently we have developed a technique to characterize the intratumor genetic heterogeneity of tumors based on sequencing data³². Using copy number and mutational data, our computational pipeline infers subclonal populations in tumors. Here, we propose to characterize the evolution of tumors under the selective pressure of rhTSH-stimulated RAI and durvalumab treatment, and examine subclonal expansions that are associated with an immune escape phenotype, by comparing the subclonal architecture of pre- and post-treatment samples.

PBMCs: In addition to the research biopsies, peripheral blood samples will be collected serially for flow cytometry to evaluate changes in T cell subsets at different time points of therapy.

Biostatistical analysis: Proportions of T cell subsets will be summarized at each time point and plotted to reveal any trend.

cfDNA: Collected cfDNA will be analyzed to detect and quantify total cfDNA and the amounts of tumor driver oncogenes (BRAF mutations, RAS mutations, etc...) or other gene mutations present

as appropriate. *Biostatistical analysis*: Changes in these parameters that occur with therapy will be analyzed by graphical method.

Accrual to the trial is anticipated to be approximately 1 patient per month.

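### The paired-biopsy analyses do not separate same-tumour from different-tumour pairs, so between-tumour differences can be mistaken for treatment-driven change

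*Combined protocol and SAP*

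**What the plan says.** **Which tumour.** Section 9.3 is the only place that addresses lesion identity for the second biopsy: "Biopsy of the same tumor that was sampled previously is preferred, but not required".

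**When.** Section 9.3 says "it is preferred that the procedure be performed during Cycle 2, Week 3 or 4", but also that "alternate timing for this second biopsy during Cycle 2 or later is allowed per investigator discretion or for safety reasons related to RAI administration". No latest time is given. Footnote n to the Section 10 calendar repeats this timing and is silent on which tumour is sampled. Section 9.5 describes the schedule more narrowly: "biopsies will be performed pre-treatment and after durvalumab/RAI in Cycle 2". Section 8.1 lets the first biopsy be taken at any time before treatment starts, including more than four weeks before.

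**What is analysed.** Section 9.5 defines the set by the existence of two biopsies and nothing else: "For patients in whom two serial research biopsies are obtained, evolution of the mutation, neoantigen, and gene expression landscape in pre- and post-treatment samples". The stated aim is to learn about immunoediting and critical epitopes. Section 14.0 repeats that aim. It also proposes to characterise how tumours evolve under selection by the study treatment, including expansions linked to immune escape, "by comparing the subclonal architecture of pre- and post-treatment samples". For summary statistics, "continuous pre- and post-treatment measures will be summarized by mean and standard deviation of the change", with 2-by-2 tables for categorical measures and graphs.

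**What is accepted about heterogeneity.** Section 3.0 says of RAI uptake that "the degree of avidity encountered varies broadly from patient to patient, and indeed tumor to tumor". Its rationale for the combination also counts on RAI acting at several sites to expose the varied neoantigens of heterogeneous disease.

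**The concern.** A pre/post pair isolates change over treatment only if the two samples would have looked alike without treatment. Two biopsies of one tumour approximate that. Biopsies of two different tumours do not: a mutation private to the first tumour appears as a loss, and a clone private to the second appears as an expansion. These are the patterns that Sections 9.5 and 14.0 set out to interpret as immunoediting and immune escape.

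Timing adds a second, lesser ambiguity. A sample taken in Cycle 2 and one taken many cycles later may describe different stages of the response, and the plan does not distinguish them.

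At stake is the interpretability of the paired tissue. Section 9.5 presents serial biopsies as the only way to learn how this treatment alters the tumour genome and immune environment, and patients must agree to two biopsies to enter. With 11 patients planned, and fewer pairs wherever a biopsy is exempted, a few unlike pairs can shape the picture.

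**Working it through.** The documents contain no calculation for the biopsy analyses; the only design figures in Section 14.0 concern the DLT rule and have no bearing here. The check is therefore mainly a comparison of sections.

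**Step 1: collection against analysis**

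| Feature | Collection rule | Condition in the analysis |
|---|---|---|
| Same tumour | Preferred, not required (9.3) | None (9.5, 14.0) |
| Time of second sample | Cycle 2, Week 3 or 4 preferred; Cycle 2 or later allowed (9.3, 10 footnote n) | None; 9.5 describes it as Cycle 2 |
| Time of first sample | Any time before Week 1 Day 1 (8.1) | None |
| Tumours differ within a patient | Accepted (3.0) | No stratum, label or sensitivity analysis |

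Every pair that the collection rule permits enters the analysis on equal terms.

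**Step 2: what a pair measures.** Let T be the change in a tumour over treatment and B the difference between two tumours that would exist without treatment. A same-tumour pair shows T plus sampling noise. A different-tumour pair shows T + B plus sampling noise. If k of m pairs are from different tumours, the pooled mean change is

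mean(T) + (sum of the k values of B)/m, plus averaged noise.

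Nothing in Section 14.0 identifies or removes the second term.

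**Step 3: direction, on assumed values only.** The documents give neither a between-tumour variance nor a share of mutations common to two tumours. The figures below show the mechanism and are not estimates for this trial.

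- *Apparent mutation loss.* If a proportion s of the first tumour's mutations is also present in the second, and neither treatment nor detection plays a part, the apparent loss is 1 − s. For s = 0.40, 0.60 and 0.80 this is 0.60, 0.40 and 0.20. Private mutations always count as losses, so these do not cancel across patients as positive and negative differences might.
- *Continuous measures.* If B is independent of the same-tumour change and its SD is r times the SD of that change, the SD for one different-tumour pair is multiplied by √(1 + r²). For r = 0.5, 1 and 2 this gives √1.25 = 1.12, √2 = 1.41 and √5 = 2.24.

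**Step 4: what is outside the problem.** DLT monitoring, best overall response and PFS use no paired tissue. The PBMC and cfDNA analyses use blood. Analyses relating baseline or archival tumour features to benefit need only one sample per patient.

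**The case against.** The strongest reply is that the plan already sets a sensible default, the same tumour in Cycle 2, Week 3 or 4, and departs from it for good reason. Section 9.3 cites safety after RAI, the note to the Section 10 calendar allows rescheduling for toxicity, and Section 6.2 bars biopsy of a sole RECIST target lesion. The work is exploratory and descriptive, with no test or threshold. The wording is tentative: immunoediting is something that may occur. Section 14.0 attaches no pooled statistic to the subclonal comparison, so an analyst could inspect each pair with its lesion in view.

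Most of this stands, and it limits the point. It justifies flexible collection, but not the absence of any distinction in the analysis. Inspecting pairs one by one helps only if lesion identity is recorded and used, which the plan does not state. A descriptive mean over unlike pairs still mixes two quantities.

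Several stronger readings are tempting but unsupported:

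- *That site differences will be reported as immunoediting.* The documents show only that they can be mistaken for it, with nothing planned to tell them apart.
- *That the exploratory objective cannot be answered.* It also covers blood and unpaired tissue, and same-tumour pairs remain informative.
- *That some percentage of the data reflects site and not treatment.* No share of different-tumour pairs is given. Moreover, a second sample from another tumour has also been exposed to systemic treatment, so it mixes site and treatment.
- *That the biopsied tumour must be RAI-avid.* Section 3.0 hypothesises a systemic immune effect resembling the abscopal effect, so a less avid tumour is still relevant.

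**Conclusion.** The concern holds as an analysis gap. Section 9.3 permits different-tumour pairs; Sections 9.5 and 14.0 do not distinguish them from same-tumour pairs; and Section 3.0 accepts the heterogeneity that makes the distinction matter. Between-tumour differences can therefore be mistaken for treatment-driven loss or expansion. Separately, the Cycle 2 description in Section 9.5 does not match the open-ended timing in Sections 9.3 and 10, and these should be reconciled.

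The reach is limited to the exploratory paired-tissue analyses. No size can be attached: planned accrual caps the pairs at 11, but the number completed and the number crossing tumours are unknown, and the gap has no effect if every pair proves to be same-tumour. The conclusion assumes only that some second biopsies may use the permission given. This is a cheap improvement to the plan, not a threat to the trial's main conclusions.

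**What to change.** In Sections 9.5 and 14.0:

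- Make same-tumour pairs the main set for the paired-change, immunoediting and subclonal-evolution analyses.
- Report different-tumour pairs separately, labelled as mixing site and treatment.
- Keep same-tumour pairs whose second sample came after Cycle 2, and show them by time since first durvalumab and since RAI. Dropping them would discard biopsies deferred for RAI safety.
- Record for each biopsy a lesion identifier, the date, and RAI avidity where a scan provides it.
- Reconcile the timing description in Section 9.5 with Sections 9.3 and 10.

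Timing flexibility, choice of lesion and the safety exemptions stay as they are, and no biopsy is added. The cost is some wording, three data fields and fewer pairs in the main summary. Same-tumour pairing removes the between-tumour component only; sampling variation within a tumour remains and should be acknowledged when results are described.
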